#### **9.4.4 Pregnancy test**

A serum pregnancy test ( $\beta$ -hCG) will be performed at run-in (V1) in women of childbearing potential, and a urine dipstick pregnancy test will be performed at V2 prior to randomization and every 4 weeks. A negative result must be obtained at V1 and V2 prior to randomization. In case of positive urinary test the study treatment will be withheld and a serum pregnancy test to confirm the pregnancy should be performed as soon as possible. Pregnancy will lead to definitive treatment discontinuation in all cases.

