## 10.3 HANDLING OF PATIENT TEMPORARY OR PERMANENT TREATMENT DISCONTINUATION AND OF PATIENT STUDY DISCONTINUATION

The IMP should be continued whenever possible. In case the IMP is stopped, it should be determined whether the stop can be made temporarily; permanent IMP discontinuation should be a last resort. Any IMP discontinuation should be fully documented in the e-CRF. In any case, the patient should remain in the study as long as possible.

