### 10.3.1 Permanent treatment discontinuation with investigational medicinal product(s)

Permanent treatment discontinuation is any treatment discontinuation associated with the definitive decision from the Investigator or the patient not to re-expose the patient to the IMP at any time.

Patients who discontinue treatment permanently during the treatment period will be assessed as soon as possible using all procedures normally planned for the End-of-treatment Visit with the exception of CT Scan. Patients who discontinue early during the post-treatment period will be assessed as soon as possible using all procedures normally planned for the end-of-study (EOS) Visit.

For patients in whom the surgery date is scheduled after the planned end of study, a follow up contact(s) should be performed around the time of planned surgery to document the surgery date. Surgery data will be collected only until e-CRF Closure and EOS will not be delayed.

Patients will also be instructed to:

- Return to the study site for evaluations of NPS, SNOT-22, at:
  - Week 24, Week 52: If the ETD visit occurred between Week 0-Week 16,
  - Week 52: If the ETD visit occurred between >Week 16-Week 40,
  - Week 64 (EOS): If the ETD visit occurred between >Week 40-Week 52.
- Return and have a CT Scan performed as scheduled at Week 24 and 52.

Patients who discontinue prior to week 40 will have the following assessed through week 52, patients who discontinue after week 40 will have the following assessed through week 64:

- Perform PK and ADA sampling at the initially scheduled visits for these assessments
- Continue to complete the e-diary for nasal congestion, loss of smell daily symptom and anterior/posterior rhinorrhea evaluation
- Continue on MFNS stable dose but patients are not required to complete the INCS use daily in the e-diary after ETD.
- Advise patients with comorbid atopic conditions (such as asthma) not to adjust their treatment without consultation with their physicians.
- Report any AE up to the last scheduled visit (Week 52 or Week 64 depending on the discontinuation date).
- Contact the Investigator during the post treatment period up to the EOS visit if the symptoms worsen requiring medical attention.

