### 10.3.3 List of criteria for permanent treatment discontinuation

The patients may withdraw from treatment with the IMP if they decide to do so, at any time and irrespective of the reason, or this may be the Investigator's decision. All efforts should be made to document the reasons for treatment discontinuation and this should be documented in the e-CRF.

Patients must be withdrawn from the study (ie, from any further IMP or study procedure) for the following reasons:

- At their own request or at the request of their legally authorized representative (legally authorized representative means an individual or judicial or other body authorized under applicable law to consent on behalf of a prospective patient to the patient's participation in the procedure(s) involved in the research).
- If, in the Investigator's opinion, continuation in the study would be detrimental to the patient's well-being.

In case of surgery for NP (refer to [Section 9.2.1.5](#) for details).

- At the specific request of the Sponsor.
- In the event of a critical protocol deviation, at the request of the Investigator or the Sponsor.
- Any code broken requested by the Investigator will lead to permanent treatment discontinuation.
- In the event of an anaphylactic systemic allergic reaction that is related to IMP and that requires treatment.
- In the event that the patient is diagnosed with a malignancy during the study, excluding carcinoma in situ of the cervix or squamous or basal cell.
- Pregnancy.
- Any opportunistic infection, such as tuberculosis or other infections whose nature or course may suggest an immunocompromised status (refer to [Appendix I](#)).
- Serum ALT >3 ULN and total bilirubin >2ULN.
- Serum ALT >5 ULN if baseline ALT <2 ULN or ALT >8 ULN if baseline ALT >2 ULN.

Stopping rules described in [Appendix G](#) should be applied.

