### 10.3.4 Handling of patients after permanent treatment discontinuation

Patients will be followed-up according to the study procedures as specified in this protocol up to the scheduled date of study completion, or up to recovery or stabilization of any AE to be followed-up as specified in this protocol, whichever comes last.

If possible, and after the permanent discontinuation of treatment, the patients will be assessed using the procedure normally planned for the last dosing day with the IMP (EOT Visit). (Refer to [Section 10.1.14](#) Visit 10 (Week 52): End of treatment).

Patients who discontinue early from treatment may be asked to return to the clinic to have additional ADA samples collected for analysis based on the overall clinical presentation at the time of discontinuation.

Patients who permanently discontinue the study medication will be asked and encouraged to return to the clinic for and participate in follow-up assessments described in ([Section 10.3.1](#)).

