### 10.4.1.3 Adverse event of special interest

An adverse event of special interest (AESI) is an AE (serious or non-serious) of scientific and medical concern specific to the Sponsor's product or program, for which ongoing monitoring and immediate notification by the Investigator to the Sponsor is required. Such events may require further investigation in order to characterize and understand them. Adverse events of special interest may be added or removed during a study by protocol amendment.

For these AESIs, the Sponsor will be informed immediately (ie, within 24 hours), per SAE notification described [Section 10.4.4](#), even if not fulfilling a seriousness criterion.

AESIs for this study include:

- Anaphylactic or systemic allergic reactions that are related to IMP and that require treatment (refer to [Appendix H](#) for the definition of anaphylaxis).
- Severe injection site reactions that last longer than 24 hours.
- Any infection meeting at least 1 of the following criteria:
  - Any serious infection (SAE),
  - Requires parenteral (IV, IM, SC) antimicrobial therapy,
  - Requires oral antimicrobial therapy for longer than 2 weeks,
  - Is a parasitic infection,
  - Is an opportunistic infection (refer to [Appendix I](#)).

**Note:** Antimicrobial therapy refers to antibiotic, antiviral, and antifungal agents.

- Significant elevation of ALT.
  - ALT  $>5 \times$  ULN in patients with baseline ALT  $\leq 2 \times$  ULN;
  - or
  - ALT  $>8 \times$  ULN if baseline ALT  $>2 \times$  ULN
- Pregnancy occurring in a female patient entered in the clinical trial or in a female partner of a male patient entered in the clinical trial. It will be qualified as an SAE only if it fulfills 1 of the seriousness criteria (see [Section 10.4.1.2](#)).
  - In the event of pregnancy in a female participant, IMP should be discontinued.
  - Follow-up of the pregnancy in a female participant or in a female partner of a male participant is mandatory until the outcome has been determined.
- Symptomatic overdose (serious or non-serious) with IMP/NIMP
  - An overdose (accidental or intentional) with the IMP/NIMP is an event suspected by the Investigator or spontaneously notified by the patient (not based on systematic syringes or pills count) and defined as at least twice the intended dose during an interval of less than 11 days. The circumstances (ie, accidental or intentional) should be clearly specified in the verbatim and symptoms, if any, entered on separate AE forms.

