#### **10.4.3 General guidelines for reporting adverse events**

All AEs, regardless of seriousness or relationship to IMP/NIMP, spanning from the signature of the informed consent form until the end of the study as defined by the protocol for that patient, are to be recorded on the corresponding page(s) or screen(s) of the e-CRF.

Whenever possible, diagnosis or single syndrome should be reported instead of symptoms. The Investigator should specify the date of onset, intensity, action taken with respect to IMP, corrective treatment/therapy given, additional investigations performed, outcome, and his/her opinion as to whether there is a reasonable possibility that the AE was caused by the IMP or by the study procedure(s).

The Investigator should take appropriate measures to follow all AEs until clinical recovery is complete and laboratory results have returned to normal, or until progression has been stabilized, or until death, in order to ensure the safety of the patients. This may imply that observations will continue beyond the last planned visit per protocol, and that additional investigations may be requested by the monitoring team up to as noticed by the Sponsor.

When treatment is prematurely discontinued, the patient's observations will continue until the end of the study as defined in [Section 10.3.1](#).

Laboratory, vital signs or ECG abnormalities are to be recorded as AEs only if:

- Symptomatic and/or,
- Requiring either corrective treatment or consultation, and/or,
- Leading to IMP discontinuation or modification of dosing, and/or,
- Fulfilling a seriousness criterion, and/or,
- Defined as an AESI.

See [Section 10.4.6](#) for a table summarizing reporting timelines.

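### The lead-in of Protocol 10.3.3 orders withdrawal from all study procedures for six medical reasons that the rest of the protocol treats as reasons to stop study drug only (minor; wrong as written)

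*Protocol*

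**What the plan says.** The heading of Protocol 10.3.3 and its opening paragraph concern stopping the investigational product (IMP). The sentence that introduces the list goes further: "Patients must be withdrawn from the study (ie, from any further IMP or study procedure) for the following reasons". Twelve reasons follow, and the section then points to stopping rules in Appendix G.

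The general rules elsewhere point the other way:

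- 10.3: "In any case, the patient should remain in the study as long as possible".
- 10.3.1: after a permanent stop, patients return for NPS and SNOT-22 on a schedule set by when they stopped ("Week 24, Week 52: If the ETD visit occurred between Week 0-Week 16" for early stops). They also keep the e-diary going, give PK and ADA samples, report adverse events, and "Return and have a CT Scan performed as scheduled at Week 24 and 52".
- 10.3.4: "Patients will be followed-up according to the study procedures as specified in this protocol up to the scheduled date of study completion".
- 10.4.3: "When treatment is prematurely discontinued, the patient's observations will continue until the end of the study as defined in" Section 10.3.1.

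Three of the listed events have their own text, which stops the drug only. For pregnancy, 9.4.4 says "Pregnancy will lead to definitive treatment discontinuation in all cases" and 10.4.1.3 says "In the event of pregnancy in a female participant, IMP should be discontinued". For allergic reactions (10.6.1) and opportunistic infection (10.6.3), the instruction is to stop study medication permanently.

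Protocol 11.4.2.1.2 and SAP 2.4.4.1 both include data collected after treatment discontinuation in the primary analysis.

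**The concern.** The lead-in is mandatory, and its parenthesis spells out that procedures stop as well as drug. It is hard to read as loose wording for a drug stop. Sites consult this section when a serious event has just occurred.

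If it is followed literally for a patient who stops before Week 24 without surgery or systemic corticosteroids (SCS), three pieces of co-primary data are at risk: the nasal congestion (NC) diary for Days 142 to 169 (the Week 24 averaging window in SAP 2.5.2), the Week 24 NPS, and the Week 24 CT for the Lund-Mackay score (LMK), which is co-primary for Japan. Multiple imputation (MI) would then replace values that the plan meant to observe.

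Safety follow-up is exposed too. Section 10.6.1 wants ADA and PK samples near onset and resolution of an allergic reaction. Section 10.4.1.3 makes pregnancy follow-up mandatory until the outcome is known. Sections 10.3.4 and 10.4.3 follow adverse events to recovery or stabilization. Ending all procedures conflicts with each of these.

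**Working it through.** **Step 1. Sort the twelve reasons in 10.3.3.**

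- *Three contradict event-specific text and the general rules:* anaphylactic or systemic allergic reaction, pregnancy, opportunistic infection.
- *Three contradict the heading and general rules only:* malignancy, ALT with bilirubin, ALT alone.
- *Two resolve themselves:* surgery (cross-referred to 9.2.1.5, which stops treatment and keeps the patient returning) and investigator code break (the item itself names treatment discontinuation, as does 8.3.2).
- *Four can be real study exits:* the patient's request, investigator judgment of detriment, sponsor request, critical deviation.

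3 + 3 + 2 + 4 = 12. The lead-in is wrong as written for the first six.

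**Step 2. Reproduce the planned power.** Inputs are from SAP 1.3: differences 0.55 (NC), 1.24 (NPS), 7.07 (LMK); SDs 1.03, 2.11, 5.50; 240 versus 120 patients, or 180 versus 90 after 25% dropout. At 180/90, power is 98.5% for NC and 99.5% for NPS, product 98.1%. The plan states 99%, 99% and at least 98%, so its figures reproduce. If dropout were 30% to 40% (my assumption), NC power would be 97.9% to 95.9%.

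**Step 3. Shift per affected dupilumab patient.** Let f be the share of the planned effect by which the imputed value is more favourable than the true off-treatment value. The documents do not give f; I take 0 to 1. Then:

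shift = f × planned difference / 240, and SE = SD × √(1/n₁ + 1/n₂).

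| | NC | NPS | LMK |
|---|---|---|---|
| Shift, f = 1 | 0.55/240 = 0.0023 | 1.24/240 = 0.0052 | 7.07/240 = 0.029 |
| Shift, f = 0.5 | 0.0011 | 0.0026 | 0.015 |
| SE, 240/120 | 0.115 | 0.236 | 0.615 |
| SE, 180/90 | 0.133 | 0.272 | 0.710 |
| Shift/SE at f = 1 (240/120; 180/90) | 2.0%; 1.7% | 2.2%; 1.9% | 4.8%; 4.1% |

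At f = 1 the shift is 1/240 = 0.42% of the planned difference for every endpoint; at f = 0.5 it is 0.21%; at f = 0 it is nil.

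**Step 4. How many patients would matter.** At the planned effects, the number of affected dupilumab patients needed to bring z down to 1.96 is (difference − 1.96 × SE)/shift. With f = 1:

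- NC: (0.55 − 1.96 × 0.115)/0.0023, about 142 (240/120) or 126 (180/90).
- NPS: about 151 or 137.
- LMK: about 199 or 193.

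**Step 5. What softens f.** The imputation code in SAP 2.4.4.1, written for NPS, conditions on changes at Weeks 4, 8 and 16. NC has four-week averages at Days 29, 57 and 113 that can serve the same way. LMK has no such help: the flow chart in Protocol 1.2 schedules no post-baseline CT before Week 24. Protocol 4.4.2 reports improvement sustained off treatment in the proof-of-concept study, which also argues for f below 1.

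**The case against.** The strongest reply is that the protocol answers the question many times over. The very next subsection, 10.3.4, deals with patients after permanent treatment discontinuation and orders follow-up; 10.3, 10.3.1 and 10.4.3 agree. The post-treatment part of the summary asks for return visits with NPS, and for continued e-diary entries, even after discontinuation from the study, though CT is not in that list. Section 10.3.5 asks for an end-of-treatment assessment, if possible, after study withdrawal. SAP 2.2 tabulates treatment discontinuation and study withdrawal separately, so an excess of withdrawals would be visible. Nothing shows that any site has followed the lead-in.

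Most of this stands. Continued follow-up is very probably what the sponsor intended, and the loss is possible rather than certain. The NPS loss is also narrow. Section 10.3.1 schedules a Week 24 return only for stops up to Week 16, and an early-termination endoscopy from Day 141 already falls in the SAP's Week 24 window. The reply does not remove the conflict, because a mandatory instruction still stands against the rules around it.

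Three stronger readings are tempting and unsupported.

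- *The whole list is wrong.* It is not: four reasons can be real study exits and two resolve themselves.
- *Surgery or SCS patients lose co-primary data.* They do not: their later values are set to missing and the worst earlier value is carried forward.
- *The trial's power or primary result is in doubt.* The counts in Step 4 rule that out at the planned effects, and the SAP also plans copy-increment and tipping-point analyses.

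**Conclusion.** The lead-in is wrong as written for six medical reasons, and the point is minor. For anaphylactic or systemic allergic reaction, pregnancy and opportunistic infection the contradiction is with both general and event-specific text. For malignancy and the two ALT criteria it is with the heading and general rules only. Appendix G is not in the text available here, so the ALT items are judged on the main text alone.

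The number of affected patients cannot be computed. The effect of about 0.4% of the planned difference per affected dupilumab patient assumes f = 1. It is not a strict ceiling, since an off-treatment value worse than the placebo mean would exceed it, but a smaller value is more likely for NC and NPS. For LMK, conditioning on earlier post-baseline visits gives no protection. The practical weight lies as much in the safety follow-up that could be cut as in the efficacy data.

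**What to change.** Split the list in 10.3.3 under two lead-ins.

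(a) *IMP must be permanently discontinued, and the patient remains in the study and is followed per 10.3.1 and 10.3.4, for: NP surgery (see 9.2.1.5), investigator code break, anaphylactic or systemic allergic reaction, malignancy, pregnancy, opportunistic infection, and the ALT criteria.*

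(b) *Patients are withdrawn from the study for: withdrawal of consent for follow-up (10.3.5), investigator judgment that continuation in the study is detrimental, sponsor request, or a critical protocol deviation at the request of the investigator or sponsor.*

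A single sentence keeping every listed patient in the study would go too far, because it would remove sponsor request and critical deviation as study exits. A patient who asks only to stop the drug remains covered by the opening paragraph of 10.3.3 and by 10.3.1.

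The cost is a short wording amendment to one section. The medical stopping criteria and their definitions stay as they are, and no visit is added beyond those 10.3.1 already asks for.

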- E 19. Known or suspected history of immunosuppression, including history of invasive opportunistic infections (eg, histoplasmosis, listeriosis, coccidioidomycosis, pneumocystosis, aspergillosis), despite infection resolution; or unusually frequent, recurrent or prolonged infections, per Investigator's judgment.
- E 20. Active tuberculosis, latent untreated tuberculosis or a history of incompletely treated tuberculosis or non-tuberculous mycobacterial infection will be excluded from the study unless it is well documented by a specialist that the patient has been adequately treated and can now start treatment with a biologic agent, in the medical judgment of the Investigator and/or infectious disease specialist. Tuberculosis testing would be performed on a country

by country basis according to local guidelines if required by regulatory authorities or ethic committees.

- E 21. Evidence of acute or chronic infection requiring treatment with systemic antibacterials, antivirals, antifungals, antiparasitics, or antiprotozoals within 4 weeks before V1 or during the run-in period, or significant viral infections within 4 weeks before V1 that may not have received antiviral treatment.
- E 22. Live attenuated vaccinations within 4 weeks prior to Visit 1 or planned live attenuated vaccinations during the study (Refer to [Appendix A](#)).
- E 23. Patients with active autoimmune disease and/or patients using immunosuppressive therapy for autoimmune disease (eg, Hashimoto's thyroiditis, Graves' disease, inflammatory bowel disease, primary biliary cirrhosis, systemic lupus erythematosus, multiple sclerosis, and other neuro-inflammatory disease, psoriasis vulgaris, rheumatoid arthritis), or patients with high titer autoantibodies at V1 who are suspected of having high risk for developing autoimmune disease at the discretion of the Investigator or the Sponsor.
- E 24. History of malignancy within 5 years before V1, except completely treated in situ carcinoma of the cervix, completely treated and resolved nonmetastatic squamous or basal cell carcinoma of the skin.
- E 25. Known or suspected alcohol and/or drug abuse.
- E 26. Patients with a history of a systemic hypersensitivity reaction, other than localized injection site reaction, to any biologic drug.

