- E 27. Active hepatitis or patients with positive or indeterminate hepatitis B surface antigen (HBsAg), hepatitis B core antibody (HBcAb) (confirmed with presence of hepatitis B virus [HBV] deoxyribonucleic acid [DNA]), or positive hepatitis C virus antibody (HCVAb) (confirmed with presence of HCV ribonucleic acid [RNA]) at V1.
- E 28. Patients with the following liver injury related criteria at V1:
- Clinically significant/active underlying hepatobiliary disease.
- OR,**
- Alanine aminotransferase (ALT) >3 upper limit of normal (ULN).
- E 29. Abnormal laboratory values at V1:
- Creatine phosphokinase (CPK) >10 ULN
- OR,**
- Platelets <100 000 cells/mm^3.
- OR,**
- Eosinophils >1500 cells/mm^3.
- E 30. Conditions/Situations such as: Patients considered by the Investigator or any sub-Investigator as inappropriate for this study for any reason, eg.:
- Those deemed unable to meet specific protocol requirements, such as scheduled visits.
  - Those deemed unable to administer or tolerate long-term injections as per the patient or the Investigator.

- Presence of any other conditions (eg, geographic, social....) actual or anticipated, that the Investigator feels would restrict or limit the patient's participation for the duration of the study.

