#### **10.4.1.2 Serious adverse event**

An SAE is any untoward medical occurrence that at any dose:

- Results in death, or.
- Is life-threatening, or.
- Note: The term “life-threatening” in the definition of “serious” refers to an event in which the patient was at risk of death at the time of the event; it does not refer to an event which hypothetically might have caused death if it were more severe.
- Requires inpatient hospitalization or prolongation of existing hospitalization, or.
- Results in persistent or significant disability/incapacity, or.
- Is a congenital anomaly/birth defect.
- Is a medically important event.

Medical and scientific judgment should be exercised in deciding whether expedited reporting is appropriate in other situations, such as important medical events that may not be immediately life-threatening or result in death or hospitalization but may jeopardize the patient or may require medical or surgical intervention (ie, specific measures or corrective treatment) to prevent one of the other outcomes listed in the definition above.

Note: The following list of medically important events is intended to serve as a guideline for determining which condition has to be considered as a medically important event. The list is not intended to be exhaustive:

- Intensive treatment in an emergency room or at home for:
  - Allergic bronchospasm,
  - Anaphylaxis (refer to [Appendix H](#) for Definition of Anaphylaxis),
  - Blood dyscrasias (ie, agranulocytosis, aplastic anemia, bone marrow aplasia, myelodysplasia, pancytopenia, etc),
  - Convulsions (seizures, epilepsy, epileptic fit, absence, etc).
- Development of drug dependence or drug abuse.
- ALT >3 x ULN + total bilirubin >2 x ULN.
- Suicide attempt or any event suggestive of suicidality.
- Syncope, loss of consciousness (except if documented as a consequence of blood sampling).
- Bullous cutaneous eruptions.
- Cancers diagnosed during the study or aggravated during the study.
- Chronic neurodegenerative diseases (newly diagnosed) or aggravated during the study.

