#### **10.4.4 Instructions for reporting serious adverse events**

In the case of occurrence of an SAE, the Investigator or any designee must immediately:

- ENTER (within 24 hours) the information related to the SAE in the appropriate screens of the e-CRF; the system will automatically send a notification to the monitoring team after approval of the Investigator within the e-CRF or after a standard delay.
- SEND (preferably by fax or e-mail) a photocopy of all examinations carried out and the dates on which these examinations were performed, to the representative of the monitoring team whose name, fax number, and email address appear on the clinical trial protocol. Care should be taken to ensure that the patient's identity is protected and the patient's identifiers

in the clinical trial are properly mentioned on any copy of a source document provided to the Sponsor. For laboratory results, include the laboratory normal ranges.

- All further data updates should be recorded in the e-CRF as appropriate, and further documentation as well as additional information (for laboratory data, concomitant medications, patient status, etc) should be sent (by fax or e-mail) to the monitoring team within 24 hours of knowledge. In addition, every effort should be made to further document any SAE that is fatal or life threatening within a week (7 days) of the initial notification.
- A back-up plan (using a paper CRF process) is available and should be used when the e-CRF system does not work.

Any SAE brought to the attention of the Investigator at any time after the end of the study for the patient and considered by him/her to be caused by the IMP with a reasonable possibility, should be reported to the monitoring team.

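### The mandatory malignancy stop exempts squamous cell cancer of any site or stage, and the ALT stop has no branch for a baseline of exactly 2 ULN

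*Protocol*

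**What the plan says.** Section 10.3.3 of the protocol sets out when withdrawal is obligatory.

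- **Malignancy.** The patient is withdrawn if "diagnosed with a malignancy during the study, excluding carcinoma in situ of the cervix or squamous or basal cell". The exempting phrase ends there, with no organ and no stage.
- **ALT alone.** The criterion is "Serum ALT >5 ULN if baseline ALT <2 ULN or ALT >8 ULN if baseline ALT >2 ULN".
- **ALT with bilirubin.** A separate bullet requires a stop for ALT above 3 ULN together with total bilirubin above 2 ULN, whatever the baseline.
- **Judgement.** Withdrawal also follows if the Investigator thinks continuing would harm the patient, or "At the specific request of the Sponsor".

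The section closes by referring to further stopping rules in Appendix G.

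Other parts of the protocol treat the same subjects differently. For cancer history at entry, E 24 in section 7.2.3 exempts, apart from cervical carcinoma in situ, only "completely treated and resolved nonmetastatic squamous or basal cell carcinoma of the skin". Section 10.4.1.2 lists as medically important "Cancers diagnosed during the study or aggravated during the study", with no exemption. Section 10.4.1.3 (under "Significant elevation of ALT") and Table 4 use the same 5 and 8 ULN limits as the ALT stop, but divide baseline into ≤2 ULN and >2 ULN.

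**The concern.** These bullets are meant to make stopping automatic for an immunomodulating drug given for up to 52 weeks at about 130 sites. A mandatory rule should not depend on each site supplying missing words.

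On the malignancy bullet, the stopping rule is looser than the entry rule. Taken at its word, it would let dosing continue, subject to judgement, in a patient with a newly found squamous carcinoma of a non-skin site. That includes the nasal cavity, although E 08 in section 7.2.1 excludes malignant nasal cavity tumours at entry.

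On the ALT bullet, a patient with baseline exactly 2 ULN whose ALT later passes 5 ULN generates a 24-hour report as an event of special interest, yet meets neither branch of the ALT-only stop. On the literal wording, that bullet gives such a patient no stopping level at all, even above 8 ULN.

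**Working it through.** The plan states no figure on this point. The check is a comparison of wording, then a rough count for the ALT boundary.

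**1. Malignancy: limits on the exemption**

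| Place | Cancer type exempted besides cervical carcinoma in situ | Limited to skin? | Limited to nonmetastatic? |
|---|---|---|---|
| E 24, section 7.2.3 (entry) | squamous or basal cell | yes | yes |
| Section 10.3.3 (mandatory stop) | squamous or basal cell | no | no |
| Section 10.4.1.2 (serious events) | none | – | – |

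The stop is the only one of the three that frees squamous cancer of any site and stage. A squamous carcinoma that is metastatic or not on the skin therefore falls inside the exemption as written. What remains is the two judgement bullets in the same list. Reporting is not affected: for such an event section 10.4.4 tells the site to "ENTER (within 24 hours) the information related to the SAE in the appropriate screens of the e-CRF".

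**2. ALT: do the branches cover every baseline?** Let b be baseline ALT in multiples of ULN.

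| b | Section 10.3.3 stop | Section 10.4.1.3 and Table 4 report |
|---|---|---|
| 1.9 | ALT >5 ULN | ALT >5 ULN |
| 2.0 | neither branch | ALT >5 ULN |
| 2.1 | ALT >8 ULN | ALT >8 ULN |

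The sets b < 2 and b > 2 together leave out b = 2; the sets b ≤ 2 and b > 2 leave out nothing. A value of 2 ULN can enter the trial, because the numerical ALT limit in E 28 excludes only values above 3 ULN at Visit 1.

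**3. How many patients could sit on the boundary?** The documents give no distribution of baseline ALT, so the following are assumptions: results reported as whole numbers; ULN of 35, 40 or 50 U/L; and a share p of the 360 patients with baseline above 1 and up to 3 ULN, spread evenly over the 2 × ULN whole numbers in that range. One of those numbers is exactly 2 ULN, so

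expected patients at 2 ULN = 360 × p / (2 × ULN).

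For example, with p = 0.10 and ULN = 40: 360 × 0.10 / 80 = 0.45.

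| ULN (U/L) | p = 0.05 | p = 0.10 | p = 0.20 |
|---|---|---|---|
| 35 | 0.26 | 0.51 | 1.03 |
| 40 | 0.23 | 0.45 | 0.90 |
| 50 | 0.18 | 0.36 | 0.72 |

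The range is 0.18 to 1.03 patients, before requiring a later ALT above 5 ULN.

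**4. Malignancy count.** The documents give no rate for non-skin squamous carcinoma. Exposure is at most 360 patients × 52 weeks, about 360 patient-years across all arms, of which 240 patients are on dupilumab. The event is assumed to be rare.

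**The case against.** The strongest reply is that the malignancy bullet is clipped wording and nobody chose the wider exemption. The phrase lacks a noun, the protocol's only full form of it is in E 24, and its pairing with cervical carcinoma in situ repeats that list. An investigator would have to complete the phrase in an unusual way and then keep dosing a patient with visceral or metastatic cancer. There are also more safeguards than the two judgement bullets. Section 10.3.2 turns an interruption of more than 2 doses into permanent discontinuation, an independent committee reviews serious events at regular intervals (section 6.4.1), and once an investigator judges continuation harmful, withdrawal is obligatory. Finally, reporting rules are usually broader than stopping rules, so that difference alone is no fault.

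On intent and on reporting, this is right. It does not repair the rule: each safeguard is a matter of judgement or acts indirectly, whereas the purpose of the list is a stop that needs no judgement.

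On ALT, the reply is that section 10.3.3 defers to Appendix G, and section 10.4.6 says its decision trees cover raised ALT. Appendix G was not available, so it may already settle the 2 ULN case. A ≤ sign lost in conversion from PDF also cannot be fully excluded, although the sign survived in section 10.4.1.3 and Table 4. E 18, E 27 and the other limb of E 28 screen out many causes of a raised baseline, so the assumed 5% to 20% may be high. These points stand as limits on the ALT half. None touches the malignancy half.

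**Conclusion.** Both parts hold as the text stands. The malignancy exemption is wider than the protocol's own entry criterion and, followed literally, does not trigger a required stop for a non-skin or metastatic squamous carcinoma. The ALT bullet disagrees with the protocol's reporting rules at one boundary value.

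The point is minor. Few patients could be affected: up to about one at the ALT boundary under the assumptions above, fewer still who would then exceed 5 ULN, and an assumed small number of relevant cancers. Because on-study cancers and marked ALT rises are notified within 24 hours, the risk is a late or uneven stop, with little chance of an unnoticed event. Sample size, endpoints, power and type I error are untouched. The malignancy half matters more and rests on the wording alone; the ALT half is subject to what Appendix G says.

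**What to change.** In section 10.3.3, reword the exemption to *carcinoma in situ of the cervix, or nonmetastatic basal or squamous cell carcinoma of the skin*. Leave out the E 24 condition that the lesion has already been treated and has resolved, since that cannot describe a new diagnosis. In the ALT bullet, change the lower branch from <2 ULN to ≤2 ULN, so that it matches section 10.4.1.3 and Table 4, and confirm that Appendix G uses the same cut.

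The cost is two phrases in a protocol amendment and one cross-check. No visit, procedure or analysis is added.
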